6. STATISTICAL CONSIDERATIONS AND ANALYSIS PLAN

6.1 DETERMINATION OF SAMPLE SIZE

Approximately 800 patients will be randomized in this study.

6.1.1 Type I Error Control

The type I error (α) for this study is 0.05 (two-sided). Type I error will be controlled for the primary endpoint of DFS and the key secondary endpoint of OS. To control the Type I error at $\alpha=0.05$ (two-sided) for DFS and OS endpoints, the treatment arms will be compared in a hierarchical fashion as follows: If the DFS analysis results (as defined for United States registrational purposes; see Section 6.4.1) are statistically significant at $\alpha=0.05$ (two-sided), then the analysis of OS will be performed at $\alpha=0.05$ (two-sided) and the interim analysis boundaries for OS (see Section 6.9.2) will be calculated according to $\alpha=0.05$ (two-sided).

6.1.2 Primary Endpoint: Disease-Free Survival

The analysis of the primary endpoint of DFS will take place when approximately 377 DFS events have occurred and at least 12 months after the last patient is enrolled have elapsed. The estimated number of events required for the analysis is based on the following assumptions:

- Two-sided log-rank test at the 0.05 significance level (two-sided)
- 80% power
- 1:1 randomization ratio
- Median DFS for the control (observation) arm of 20 months and estimated median DFS in the atezolizumab arm of 26.7 months (corresponding to a HR of 0.75)
- No interim analysis of DFS

Accrual of the planned 800 patients is projected to occur over 32 months, assuming a ramp-up period of 13 months to a projected accrual rate of 35 patients per month. On the basis of these assumptions, and the projected probability of loss to follow-up for DFS of approximately 32% over 24 months after enrollment, the required number of DFS events is projected to occur at Month 50 from the time the first patient is randomized. Also on the basis of these assumptions, it is projected that an observed HR of 0.82 or lower will result in a statistically significant difference between treatment arms (i.e., an HR of 0.82 will be the minimally detectable difference at the analysis; this corresponds to an improvement of 4.5 months in median DFS, from 20 months in the control [observation] arm to 24.5 months in the atezolizumab arm).

6.1.3 Secondary Endpoint: Overall Survival

The final analysis of the secondary endpoint of OS will take place when approximately 428 deaths have occurred on the basis of the following assumptions:

- Two-sided log-rank test at the 0.05 significance level (two-sided)
- 80% power
- 1:1 randomization ratio
- Median OS for the control (observation) arm of 34 months and estimated median OS in the atezolizumab arm of 44.7 months (corresponding to HR of 0.76)
- Two interim analyses of OS

On the basis of these assumptions, the projected probability of loss to follow-up for OS of approximately 24% over 24 months after enrollment, and projected accrual, the required number of OS events for the final analysis of OS is projected to occur 95 months from the time the first patient is randomized. It is projected that an observed HR of 0.82 or lower will result in a statistically significant difference between treatment arms (i.e., an HR of 0.82 will be the minimally detectable difference at the analysis; this corresponds to an improvement of 7.4 months in median OS, from 34 months in the control [observation] arm to 41.4 months in the atezolizumab arm).

Two interim analyses of OS are planned; see Section 6.9 for details.

6.2 SUMMARIES OF CONDUCT OF STUDY

Enrollment, major protocol deviations including major deviations of inclusion/exclusion criteria, and reasons for discontinuation from the study will be summarized by treatment arm for the ITT population. Study treatment administration and reasons for discontinuation from the study treatment will be summarized by treatment arm for all treated patients.

6.3 SUMMARIES OF TREATMENT GROUP COMPARABILITY

Demographic variables such as age, sex, race/ethnicity, stratification factors (nodal status, number of lymph nodes resected, tumor stage, PD-L1 status, and prior neoadjuvant chemotherapy), baseline and disease characteristics (e.g., ACCI, time since initial diagnosis, time since surgery, surgery-related information, type of urinary diversion, and ECOG Performance Status) will be summarized by treatment arm for all randomized patients. Continuous variables will be summarized using means, standard deviations, medians, and ranges. Categorical variables will be summarized by proportions.

The baseline value of any variable will be defined as the last available value prior to the first administration of study treatment.

6.4 EFFICACY ANALYSES

The efficacy analyses will include all randomized patients based on the ITT principle, with patients grouped according to the treatment assigned at randomization.

6.4.1 Primary Efficacy Endpoint

The primary efficacy endpoint is investigator-assessed DFS, defined as the time from randomization to the time of first occurrence of a DFS event, defined as any of the following: local (pelvic) recurrence of UC; urinary tract recurrence of UC; distant metastasis of UC; or death from any cause. Data for patients without a DFS event will be censored at the last date the patient was assessed to be alive and recurrence free as determined with radiographic evidence. Data for patients with no post-baseline disease assessment will be censored at the randomization date.

For United States registrational purposes, the primary efficacy endpoint of DFS will be defined as described above with an additional censoring rule for missed visits. Data for patients with a DFS event who missed two or more scheduled assessments immediately prior to the DFS event will be censored at the last tumor assessment as determined with radiographic evidence prior to the missed visits. Type I error control (see Section 6.1.1) will be applied to this analysis of DFS.

DFS will be analyzed in the ITT population. The following analyses will be performed for both DFS endpoints described above. DFS will be compared between treatment arms using the stratified log-rank test. The hazard ratio (HR) for recurrence or death will be estimated using a stratified Cox proportional hazards model and the 95% CI for the HR will be provided. The stratification factors will be the same as the randomization stratification factors (see Section 4.2); however, stratification factors may be combined for analysis purposes if necessary to minimize small stratum cell sizes. Combination of stratification factors, if any, would be specified in the Statistical Analysis Plan (SAP) prior to analysis. The stratification factors will be obtained from the IxRS at the time of randomization. Results from an unstratified analysis will also be provided. Kaplan-Meier methodology will be used to estimate median DFS for each treatment arm; Kaplan-Meier curves will be produced. Brookmeyer-Crowley methodology will be used to construct the 95% CI for the median DFS for each treatment arm. The DFS rate at various timepoints (i.e., every 6 months after randomization) will be estimated by Kaplan-Meier methodology for each treatment arm, and the 95% CI will be calculated using Greenwood's formula.

The following additional analyses will be performed for both DFS endpoints described above:

- Analyses at landmark timepoints, described in Section 6.8.1
- Subgroup analyses, described in Section 6.8.2

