3.4 OUTCOME MEASURES

3.4.1 Efficacy Outcome Measures

3.4.1.1 Primary Efficacy Outcome Measure

The primary efficacy outcome measure for this study is as follows:

- Investigator-assessed DFS, defined as the time from randomization to the time of first occurrence of a DFS event, defined as any of the following:
 - Local (pelvic) recurrence of UC (including soft tissue and regional lymph nodes)
 - Urinary tract recurrence of UC (including all pathological stages and grades)
 - Distant metastasis of UC
 - Death from any cause

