6.4.2.3 Distant Metastasis-Free Survival

DMFS is defined as the time from randomization to the date of a DMFS event, defined as diagnosis of distant (i.e., non-locoregional) metastasis or death from any cause. Data for patients without a DMFS event will be censored at the last date the patient was assessed to be alive and free of distant metastasis. Data for patients with no post-baseline disease assessment will be censored at the randomization date. Methods for comparison of DMFS between treatment arms will be the same as the methods for treatment comparison for the primary efficacy endpoint of DFS.

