4.4.1 Primary Efficacy Endpoint

The primary efficacy endpoint is Investigator-assessed DFS, defined as the time from randomization to the first occurrence of a DFS event, defined as any of the following:

- Local (pelvic) recurrence of UC
- Urinary tract recurrence of UC
- Distant metastasis of UC
- Death from any cause

Data for patients without a DFS event will be censored at the last date the patient was assessed to be alive and recurrence free as determined with radiographic evidence. Data for patients with no post-baseline disease assessment will be censored at the randomization date.

For U.S. registrational purposes, the primary efficacy endpoint of DFS will be defined as described above with an additional censoring rule for missed visits. Data for patients with a DFS event who missed two or more consecutive scheduled assessments immediately prior to the DFS event will be censored at the last date the patient was assessed to be alive and recurrence free as determined with radiographic evidence prior to the missed visits or at the randomization date if there is no post-baseline tumor assessment prior to the DFS event.

DFS will be analyzed in the ITT population. The following analyses will be performed for both DFS endpoints described above. Treatment comparisons will be based on the stratified log-rank test at the two-sided level of significance as described in Section 2.2.1. The stratification factors used for the analysis are described in Section 4.4 and the values will be those recorded in the IxRS. The null and alternative hypotheses can be phrased in terms of the survival functions $S_A(t)$ and $S_B(t)$ in Arm A (atezolizumab) and Arm B (observation), respectively:

$$H_0: S_A(t) = S_B(t) \text{ versus } H_1: S_A(t) \neq S_B(t)$$

The HR, λ_A/λ_B , where λ_A and λ_B represent the hazard of experiencing an DFS event in Arm A and Arm B, respectively, will be estimated using a stratified Cox regression model with the same stratification variables used for the stratified log-rank test, and the 95% CI for the HR will be provided. Results from an unstratified analysis will also be provided.

Kaplan-Meier methodology will be used to estimate median DFS for each treatment arm and to construct DFS curves for each treatment arm. The Brookmeyer-Crowley methodology will be used to construct the 95% CI for the median DFS for each treatment arm (Brookmeyer and Crowley 1982).

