4.4.2.3 Distant Metastasis-Free Survival (DMFS)

DMFS is defined as the time from randomization to the date of a DMFS event, defined as diagnosis of distant (i.e., non–locoregional) metastasis or death from any cause. Data for patients without a DMFS event will be censored at the last date the patient was assessed to be alive and free of distant metastasis. Data for patients without post baseline disease assessment will be censored at the randomization date. Methods for comparison of DMFS between treatment arms will be the same as the methods for treatment comparison for the primary efficacy endpoint of DFS.

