4.4.2.4 Non-Urinary Tract Recurrence-Free Survival (NURFS)

NURFS is defined as the time from randomization to the date of a NURFS event, defined as diagnosis of non-urinary tract (non–UT) recurrence (i.e., pelvic soft tissue or regional lymph node recurrence, or distant metastasis) or death from any cause. Data for patients without a NURFS event will be censored at the last date the patient was assessed to be alive and free of non–urinary tract recurrence. Data for patients with no post baseline disease assessment will be censored at the randomization date day. Methods for comparison of NURFS between treatment arms will be the same as the methods for treatment comparison for the primary efficacy endpoint of DFS.

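### The sentence censoring patients with no post-baseline assessment at randomization is not limited to event-free patients; read literally, it conflicts with death being a DFS, DMFS and NURFS event

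*Protocol*

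**What the plan says.** Protocol Section 6.4.1 defines a DFS event as "local (pelvic) recurrence of UC; urinary tract recurrence of UC; distant metastasis of UC; or death from any cause". No scan is required before a death counts. Two censoring sentences follow. The first is confined to patients with no event: "Data for patients without a DFS event will be censored at the last date the patient was assessed to be alive and recurrence free". The second is not: "Data for patients with no post-baseline disease assessment will be censored at the randomization date".

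The other endpoints follow the same pattern. DMFS (Protocol Section 6.4.2.3) is "defined as diagnosis of distant (i.e., non-locoregional) metastasis or death from any cause", and NURFS (Section 6.4.2.4) also counts any death. Both carry the same unconfined second sentence. Section 6.4.3 and the protocol synopsis repeat it for DFS.

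SAP Section 1 says that the SAP's analyses supersede the protocol's, but the SAP keeps the wording:
- DFS, Section 4.4.1: "Data for patients with no post-baseline disease assessment will be censored" at randomization.
- DMFS, Section 4.4.2.3: "Data for patients without post baseline disease assessment will be censored at the randomization date".
- NURFS, Section 4.4.2.4: "Data for patients with no post baseline disease assessment will be censored at the randomization date day".

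SAP Section 4.9 on missing data only refers back to these sections.

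**The concern.** The first scheduled recurrence assessment is 12 weeks after randomization (Protocol Section 3.1). A patient who dies at Week 8 without an unscheduled scan meets the event definition and also the condition for Day 0 censoring. The two rules give opposite results, and neither document says which prevails.

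A patient censored at time zero enters no risk set and contributes nothing to the log-rank test or the Cox model. The US version of DFS is the general definition plus one further censoring rule, so it inherits the conflict, and Protocol Section 6.1.1 makes that version the gate to the OS test. The trial is open-label, so the choice should not be left until the data are in hand.

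**Working it through.** **1. The plan's own event count.** Inputs from Protocol Section 6.1.2: median DFS 20 and 26.7 months, two-sided alpha 0.05, 80% power, 1:1 allocation. Schoenfeld: d = 4(1.960 + 0.842)² / (ln HR)², with HR = 20/26.7. This is 31.40 / 0.0835 = 376.1, rounded up to 377. The stated figure is reproduced, and power at 377 events is 80.1%.

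**2. Loose ceiling on deaths by Week 12.** Inputs: median OS 34 and 44.7 months (Section 6.1.3), 400 patients per arm, exponential survival (an assumption). Week 12 is 12 × 7 / 30.4375 = 2.76 months.
- Observation: 400 × [1 − exp(−ln 2 × 2.76/34)] = 400 × 0.0547 = 21.9.
- Atezolizumab: 400 × [1 − exp(−ln 2 × 2.76/44.7)] = 400 × 0.0419 = 16.8.
- Total 38.6, about 39, or 10% of 377.

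This counts every death by Week 12, including any that followed an unscheduled scan. It does not count a patient who misses the Week 12 scan and dies later with no scan at all; the documents give no basis for that number.

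**3. Assumed range.** The documents give no count of deaths before the first scan. At 0.5%, 1% and 2% of 800 it is 4, 8 and 16 patients, or 1.1%, 2.1% and 4.2% of 377.

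**4. Power if the events were lost and not replaced** (HR 20/26.7):

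| Deaths dropped | Power |
|---|---|
| 0 | 80.1% |
| 4 | 79.7% |
| 8 | 79.3% |
| 16 | 78.4% |
| 39 | 75.7% |

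The analysis is triggered by events, so in practice the main effect of losing some would be on timing.

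**5. Direction.** With near-equal numbers at risk, early deaths add about (Arm A deaths − half of all early deaths) to the log-rank numerator; a negative value favours atezolizumab. The figures in step 2 give 16.8 − 38.6/2 = −2.5, so dropping those deaths removes evidence in the drug's favour. An equal split adds about zero. Only an excess in Arm A gives a positive term, whose removal would favour the drug.

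**6. Size of the toxicity case.** Table 3 in Protocol Section 1.2.2.2 reports treatment-related Grade 5 events in 1 of 119 and 0 of 310 patients, or 1/429 = 0.23%. Carried over to 400 Arm A patients (an assumption, since these were metastatic patients and the events were not limited to 12 weeks), that is 0.9, about one death.

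**The case against.** The strongest reply is that the sentence was meant for event-free patients all along. Much supports this:
- The sentence before it sets censoring for patients without an event at their last assessment, and this one supplies a date when there is no such assessment.
- The US clause in SAP Section 4.4.1 deals separately with patients who do have an event. After two or more consecutive missed assessments, it censors them at randomization if no scan preceded the event. That would be largely redundant if the general sentence already covered them. A patient who dies before Week 12 has missed no scheduled assessment, so the clause does not reach that death.
- The OS rule in SAP Section 4.4.2.1 has the same two-step form, and there the Day 0 fallback plainly concerns patients not known to have died.

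This stands as evidence of intent, so a reader who infers that the plan deletes early deaths goes further than the documents allow. It does not settle the text. The protocol's US rule has no such clause: for a patient with an event and no scan it names no usable date, and only the general sentence would supply one. In that document the sentence could reach a patient with an event.

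It is also fair that the consequences are contained. OS counts every death, and the safety analyses summarize deaths and their causes, so early fatal toxicity would remain visible. Entry requires a life expectancy of at least 12 weeks, and suspected recurrence calls for prompt unscheduled imaging (Protocol Section 4.5.5). Both push the true number below 39.

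**Conclusion.** The point holds as a conflict between two stated rules in the primary endpoint and two secondary ones. It does not establish that deaths will be dropped; the context favours counting them, but no sentence says so.

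The likely size is small: 4 to 16 patients if 0.5% to 2% die before a first scan, which is an assumed range. The figure of 39, or 10% of events, rests on a constant hazard from Day 0 and should not be read as an expected loss.

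A reader might also infer that the rule biases DFS toward atezolizumab, because early fatal drug toxicity can occur only in Arm A. The documents do not support that as a general statement. Under the planning medians the literal rule drops about 22 control deaths and 17 atezolizumab deaths. It would favour atezolizumab only if early deaths were in excess in Arm A, and the plan's own background data suggest about one treatment-related death per 400 patients. OS is not affected.

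**What to change.** Replace the sentence with one to this effect: *patients with neither an event nor a post-baseline disease assessment are censored at randomization; a death before the first post-baseline disease assessment is an event on the date of death*. For the US version of DFS, add that this is subject to the two-missed-assessments rule, and give the protocol's US rule the same fallback date as the SAP's.

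The places are SAP Sections 4.4.1, 4.4.2.3 and 4.4.2.4, which take precedence; Protocol Sections 6.4.1, 6.4.2.3, 6.4.2.4 and 6.4.3; and the protocol synopsis.

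The cost is one sentence per place. No new data are needed and the 377-event target stays. If event-first was always intended, no result changes.

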6.4.2 Secondary Efficacy Endpoints

6.4.2.1 Overall Survival

OS is defined as the time from randomization to the date of death from any cause, regardless of whether the death occurs during study treatment or following treatment discontinuation. Data for patients who have not died will be censored at the last date they were known to be alive. Methods for comparison of OS between treatment arms will be the same as the methods for treatment comparison for the primary efficacy endpoint of DFS.

Three analyses of OS are planned (two interim analyses and one final analysis; see Section 6.9 for details). The first interim analysis of OS will occur at the time that the primary endpoint of DFS is analyzed. The type I error control for the secondary endpoint of OS is described in Section 6.1.1.

6.4.2.2 Disease-Specific Survival

DSS is defined as the time from randomization until the date of death from UC. Data for patients who have not died will be censored at the last date they were known to be alive. Data for patients who died from causes other than UC will be censored at the date of death. Methods for comparison of DSS between treatment arms will be the same as the methods for treatment comparison for the secondary efficacy endpoint of OS.

For the purposes of evaluating DSS, for each patient death, the cause of death will be assessed as related or not related to UC by the investigator.

6.4.2.3 Distant Metastasis-Free Survival

DMFS is defined as the time from randomization to the date of a DMFS event, defined as diagnosis of distant (i.e., non-locoregional) metastasis or death from any cause. Data for patients without a DMFS event will be censored at the last date the patient was assessed to be alive and free of distant metastasis. Data for patients with no post-baseline disease assessment will be censored at the randomization date. Methods for comparison of DMFS between treatment arms will be the same as the methods for treatment comparison for the primary efficacy endpoint of DFS.

6.4.2.4 Non-urinary Tract Recurrence-Free Survival

NURFS is defined as the time from randomization to the date of a NURFS event, defined as diagnosis of non-urinary tract recurrence (i.e., pelvic soft tissue or regional lymph node recurrence, or distant metastasis) or death from any cause. Data for patients without a NURFS event will be censored at the last date the patient was assessed to be alive and free of non-urinary tract recurrence. Data for patients with no post-baseline disease assessment will be censored at the randomization date. Methods for comparison of NURFS between treatment arms will be the same as the methods for treatment comparison for the primary efficacy endpoint of DFS.

6.4.3 Handling of Missing Data

For DFS, data for patients without a DFS event will be censored at the last date the patient was assessed to be alive and recurrence free. Data for patients with no post-baseline disease assessment will be censored at the randomization date. In the analysis of DFS for United States registrational purposes, data for patients with a DFS event who missed two or more scheduled assessments immediately prior to the DFS event will be censored at the last tumor assessment with radiographic evidence prior to the missed visits (see Section [6.4.1](#)).

For OS, data for patients not reported as having died will be censored on the date last known to be alive.

For DSS, data for patients without a DSS event will be censored at the last date the patients were assessed to be alive and free of UC.

For DMFS, data for patients without a DMFS event will be censored at the last date the patients were assessed to be alive and free of distant metastasis.

For NURFS, data for patients without a NURFS event will be censored at the last date the patients were assessed to be alive and free of non-urinary tract recurrence.

